#### 2.6 Potential Risks and Benefits

#### 2.6.1 Potential Risks

#### 2.6.1.1 Biological Risks: LACTIN-V and Placebo

The study product contains a naturally occurring strain of *L. crispatus* CTV-05. To date, there has been considerable amount of experience using LACTIN-V at concentrations up to  $2 \times 10^9$  cfu/dose without any apparent related adverse effects, with the exception of a short duration of asymptomatic vaginal discharge. No serious adverse events have been reported in Protocol No. LV-001, LV-002 and LV-004 using LACTIN-V at 5 x 10^6 and 5 x 10^8 cfu/dose, and no subject left the protocol due to an adverse event. No severe or severe-related adverse event has been experienced by more than one subject. In Protocol No. LV-003, using LACTIN-V at 5 x 10^8 cfu/dose, one subject in the placebo group experienced three simultaneous SAEs unrelated to LACTIN-V. Two subjects in the LACTIN-V group discontinued study treatment due to AEs; one subject became pregnant and the other reported nausea and diarrhea, which required treatment.

Safety results of the recently completed Phase 2a trial (LV-006) assessed colonization efficiency, safety, tolerability and acceptability of LACTIN-V at 2 x 10^9 cfu/ dose in 24 women with BV. No Grade 3 AEs or SAEs were observed during the clinical phase of the study. Based on the DAIDS Toxicity Table Addendum for Vaginal Microbicide Studies (November 2007)  designed to standardize AE assessment, a total of 120 total AEs were reported, 108 (90%) of which were Grade 1 and 12 (10.0%) were Grade 2 severity. The most common genitourinary AEs included vaginal discharge of study product (46%), abdominal pain (46%) and dysuria (21%). AEs were evenly distributed between LACTIN-V and placebo groups. All enrolled women (n=24) reported at least one AE. A single participant receiving placebo discontinued herself from study product due to a moderate AE (vaginal irritation).

Risks from the administration of LACTIN-V are low since colonization with this type of organism is strongly associated with improved vaginal health. No systemic risks are anticipated since this is an organism that is applied topically and not expected to be absorbed. These risks will be explained in the written informed consent form. No pregnant women, fetuses, prisoners, children, persons with an active STI or women undergoing in vitro fertilization are included in this study.

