#### 4:

The proportion of subjects with cervicotypes I-IV compared by study arm.

Primary / Secondary Outcome Safety Measures for Objective 3 (safety and acceptability)

Safety of LACTIN-V and the applicator will be measured by:

The proportion of participants reporting product-related AEs and SAEs through the final visit that are likely related to use of study product compared by study arm, in particular Grade 3 AEs and SAEs.

Acceptability of LACTIN-V and the applicator will be measured by standardized questionnaire about acceptability of the study product and participants' stated willingness to use this type of product in the future, in each study arm.

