## 4.0 STUDY DESIGN

This is a Phase 2 randomized double-blind placebo-controlled trial to assess the impact of the live biotherapeutic product LACTIN-V containing *Lactobacillus crispatus* CTV-05 on the vaginal microbiome of young women in South Africa at high risk of HIV acquisition.

The study will also assess the safety of LACTIN-V by comparing the incidence of AEs between women randomized to LACTIN-V or placebo.

We will conduct a randomized, placebo-controlled trial of LACTIN-V in a cohort of young South African women with a non-*Lactobacillus* dominant microbiota, who are sexually experienced, age 18 to 23 years. Enrolment will be continued until 60 women will be randomized into the study.

Eligible women will be treated with oral metronidazole 400 mg twice daily for seven days and will then be randomized 2:1 to LACTIN-V vs. placebo.

Within 8-48 hours of taking the final metronidazole dose, women will receive the study product for five consecutive days, followed by a twice weekly dose for three additional weeks.

After enrolment and metronidazole treatment, women will be followed throughout the 4 weeks of dosing and the 4 weeks of post-dosing phase for a total of 10 weeks (until approximately Day 64).

The primary outcome (**Objective 1**) focuses on the ability of the *L. crispatus* CTV-05 to acutely decrease genital tract inflammation (as a marker of HIV susceptibility). This will be assessed by collecting cervicovaginal fluid and endocervical immune cells at randomization (Day 8), after 4 weeks of treatment with the LACTIN-V vs. placebo (Day 36), and after 4 weeks of post-dosing phase (Day 64).

Direct anti-HIV activity will be assessed with *in vitro* HIV infection assays using vaginal fluid samples from randomization and after treatment: Randomization Visit (Day 8), Follow-up Visit (Day 36), and Final Visit at Day 64.

A secondary outcome (**Objective 2**) is to assess the ability of the *L. crispatus* CTV-05 to establish durable vaginal colonization as with the potential as a self-sustaining prevention strategy. This will be assessed by characterization of the vaginal microbiome at the baseline FRESH Study Visit, and the end of treatment (Day 36) and at the Final Visit (Day 64), after 4 additional weeks during the post-treatment phase.

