## 11.4 Safety Analysis

This study will be monitored for safety and to determine if any of the safety halting rules described in detail in Section 9.5 are met (one or more treatment-related SAE, two or more treatment-related vaginal ulceration, two or more treatment-related severe Grade 3 systemic adverse events). Thus, all patients will be evaluated for toxicity. The DSMB will review interim analyses comparing product-related AEs between the two treatment arms will be performed after half of the 60 participants complete the Follow-Up Study Visit 11, and then annually. Reports of these analyses will be sent to the Principal Investigator or Senior Investigators at the participating institutions.

The table below gives the probability of observing at least one incidence of AE together with the corresponding true AE rate for a total of 60 participants.

True AE rate:	0.5%	1%	2%	5%
P [AE>1]:	0.26	0.45	0.70	0.95

For example, the probability of observing at least one incidence of AE with true rate of 5% is 0.95.

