Sparse clustering, where clustering and feature selection are integrated, will be used to identify study subjects with similar microbial profiles. Sparse clustering has a number of advantages. If the underlying groups differ only in terms of some of the features, then it might result in more accurate identification of these groups than standard clustering. It also yields interpretable results, since one can determine precisely which features are responsible for the observed differences between the groups or clusters. Similarly, Sparse Principal Component analysis will be used to group a set of highly correlated microbial reads to uncorrelated summary variables. As in Objective 1, adjustment for multiple testing will be made using less conservative multiple testing correction methods (e.g., Benjamini-Hochberg).

Solicited AEs will be analyzed by taking the most severe response over the Day 64 followup period. The analyses of AEs and SAEs is mainly descriptive. Descriptive measures (frequency and percent) will be used to summarize the proportion of participants with product-related AEs (Grade 0, Grade 1, Grade 2, and Grade 3) in each treatment arm. Confidence intervals for AEs rates will be estimated using methods for exact binomial confidence intervals. Fisher's exact test will be used to compare rates of AEs between the two treatment arms. Multivariate analyses using logistic regression models will be used to compare AEs rates between the two arms while adjusting for the effect of other covariates.

Unsolicited AEs will be coded by MedDRA® for preferred term and system organ class. The proportion of participants and exact 95% confidence intervals of AEs in aggregate, as well as by MedDRA® categories, will be computed. The number of SAEs will be reported by a detailed listing showing the type, MedDRA® coding, relevant dates (treatment dosing dates and AE onset and resolution dates), severity, relatedness, and outcome for each event.

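### The safety outcome, the by-arm AE table and the DSMB interim comparison are limited to product-related AEs, so an all-cause comparison by arm is not required at the interim and only ambiguously planned at the end

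*Combined protocol and SAP*

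**What the plan says.** Some statements are limited to events the clinician attributes to the product:

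- Section 3.4.1, Objective 3: the safety measure is the proportion of participants with AEs and SAEs "that are likely related to use of study product compared by study arm, in particular Grade 3 AEs and SAEs".
- Section 11.2, Objective 3: the outcome is again treatment-related AEs, with emphasis on Grade 3.
- Section 11.4: "The DSMB will review interim analyses comparing product-related AEs between the two treatment arms", once half of the 60 women have completed Visit 11.
- Section 9.6: the board's aggregate review looks for a raised rate of serious suspected reactions.
- Section 11.5, descriptive table: frequencies and percentages will "summarize the proportion of participants with product-related AEs", by grade (0 to 3) and by arm.

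Others carry no such limit:

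- Section 4.0: safety is assessed by "comparing the incidence of AEs between women randomized to LACTIN-V or placebo".
- Section 11.5, two sentences after the descriptive table: "Fisher's exact test will be used to compare rates of AEs between the two treatment arms", and then "Multivariate analyses using logistic regression models will be used to compare AEs rates between the two arms".
- Section 9.6: the board's meetings are to assess safety and efficacy by arm, with the data elements left to a charter that is not part of these documents.
- Section 9.2.2: every SAE goes to the DSMB, whatever its relatedness.

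Two further statements in 11.5 are silent on the comparison. Unsolicited AEs are summarised overall and by MedDRA category with exact intervals, but no split by arm is stated. SAEs are reported as a listing, with relatedness as one field.

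**The concern.** In a double-blind placebo-controlled trial, comparing all AEs between randomised arms does not depend on anyone's view of cause. Limiting the comparison to related events puts a clinician's binary judgement (9.2.1) between the event and the analysis. Every woman here has just taken metronidazole, and many of the AEs listed in 9.2.1, such as nausea, discharge and itching, have ready alternative explanations. A real excess on LACTIN-V that was mostly put down to something else would be thinned out, or removed, before the arms were compared.

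The internal conflict matters as well. Two analysts could follow this text and produce different primary safety tables, one of all AEs and one of related AEs, and each could cite a section in support. At the interim, a DSMB report that met section 11.4 to the letter need contain no all-cause comparison by arm.

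**Working it through.** **1. The plan's own figures.** Section 11.4 tabulates the chance of at least one AE among 60 women, which is 1 − (1 − r)^60. For r = 0.5%, 1%, 2% and 5% this gives 0.260, 0.453, 0.702 and 0.954, against the stated 0.26, 0.45, 0.70 and 0.95. Section 11.3 states more than 88% power for 10% v 50% with 20 v 40 women by two-sided Fisher's exact test at 5%. Exact enumeration gives 0.891. Both reproduce, and neither is in dispute.

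**2. What is required at each look.**

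| Look | Related events, by arm | All AEs, by arm |
|---|---|---|
| DSMB interim | Required (11.4) | Not required; general wording in 9.6, content left to the charter |
| Final, descriptive | Required (11.5) | Not stated; unsolicited AEs have no arm split, SAEs are listed |
| Final, tests | Outcome in 3.4.1 and 11.2 | Fisher and logistic sentences in 11.5 have no limit, but follow the related-only table in the same paragraph |

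**3. How much the filter could cost.** The documents give no AE rates by arm for this comparison, so the rates below are assumptions. Let the all-AE proportions be 20% on placebo and 60% on LACTIN-V. Let q be the fraction of affected women in each arm with at least one event judged related. The related-only proportions are then 0.20q and 0.60q. Power is for exact two-sided Fisher at 5%, with 20 v 40 at the end and about 10 v 20 at the interim (30 women, 2:1).

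| q | Related-only rates | Final power | Interim power |
|---|---|---|---|
| 1 (all AEs) | 20% v 60% | 0.81 | 0.45 |
| 0.75 | 15% v 45% | 0.61 | 0.30 |
| 0.5 | 10% v 30% | 0.37 | 0.10 |
| 0.25 | 5% v 15% | 0.10 | 0.004 |

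Starting from 20% v 50%, final power is 0.57 on all AEs and 0.23 at q = 0.5.

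**4. The opposite case.** Suppose product-caused AEs occur in 10% v 50% and are attributed perfectly, and unrelated AEs occur independently at rate b in both arms. The all-AE proportions are 1 − 0.9(1 − b) and 1 − 0.5(1 − b). Related-only power is 0.89 throughout.

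| b | All-AE rates | All-AE power (20 v 40) |
|---|---|---|
| 30% | 37% v 65% | 0.46 |
| 50% | 55% v 75% | 0.31 |
| 70% | 73% v 85% | 0.16 |
| 90% | 91% v 95% | 0.07 |

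A high background is plausible here. Of the earlier Phase 2a trial (LV-006), section 2.6.1.1 reports: "All enrolled women (n=24) reported at least one AE". Neither comparison is better under all conditions, so both should be shown.

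**The case against.** The strongest reply is that the final all-cause comparison is already in the plan. The Fisher and logistic sentences in 11.5 speak of AEs without qualification, and section 4.0 commits to comparing AE incidence between arms. That stands as far as it goes. A reader might infer that the final analysis omits an all-AE comparison altogether, and the documents do not support that. What remains is ambiguity: those sentences come straight after a related-only table, and they serve outcomes that 3.4.1 and 11.2 define as related events.

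For the DSMB, all SAEs reach the board (9.2.2), section 9.6 speaks generally of safety by arm, and section 5.3.2 allows data by treatment group. So the board is not confined to related events. Still, the only between-arm AE comparison actually specified for the interim is the related one, and no section requires the wider one.

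A reader might also infer that the filter biases the comparison, or that it always loses power. Neither follows. Study personnel who perform assessments are blinded (5.3.2), so errors of attribution should be similar in the two arms. The filter can remove background noise as well as signal, as step 4 of the working shows. Nor does the overall summary of unsolicited AEs say that the arms are pooled; it is silent on the split.

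**Conclusion.** The point holds as an inconsistency to be resolved. The safety outcome measures, the by-arm descriptive table and the one specified interim comparison are limited to attributed events, while the design statement and the final tests are not. An all-cause comparison by arm is therefore not required at the interim and only ambiguously planned at the end.

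The size cannot be fixed from the documents. On the assumed rates of 20% v 60%, final power falls from 81% to 61% or 37% when three quarters or half of affected women have an event judged related. On the assumed product-caused rates of 10% v 50% with unrelated background of 30% to 90%, the related-only comparison is the stronger one (89%, against 46% down to 7%). These figures support presenting both sets of events. They do not support dropping or demoting the related-only analysis. Because all AEs are recorded regardless of relationship (9.2.1), no information is lost for good, and this is a low-cost improvement rather than a flaw that threatens the trial.

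**What to change.** In sections 3.4.1, 11.2, 11.4 and 11.5, state that all AEs and SAEs, solicited and unsolicited, will be tabulated and compared by arm and by grade regardless of relatedness, in the DSMB interim report and in the final analysis. Show product-related AEs alongside as a subset. In 11.5, say which set of events the Fisher and logistic analyses cover, and give the unsolicited-AE summary an explicit split by arm. The DSMB charter should list the same tables.

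The cost is wording and a few more table shells; data collection and sample size do not change. The drawback is that the all-AE comparison may be diluted by background events, which is the reason for keeping both the related subset and the split by grade.

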# 11.3 Sample Size Considerations

The study will accrue a total of 60 randomized subjects (n=20 for the placebo arm A and n=40 for the LACTIN-V arm B). The accrual for this study is expected to be completed within 75 weeks (18 months) with projected accrual rate of 3 subjects per month. Each subject will be followed up for 64 days.

The primary endpoint upon which the sample size calculation was based is the proportion of subjects with a  $\geq 1 \text{ Log}_{10}$  decrease in at least 3 of 9 proinflammatory cytokines in CVL specimens on the Day 36 Visit, i.e. at the completion of the LACTIN-V/Placebo dosing phase. The proportion of women with decreased inflammation will be compared between the two study arms. This endpoint is adapted from the CAPRISA 004 study which demonstrated that women with the highest levels of at least 3 of 9 proinflammatory cytokines in CVL specimens had an increased risk of HIV acquisition. Our adaptation of the CAPRISA 004 analysis is that we will define "decreased inflammation" as a  $\geq 1 \text{ Log}_{10}$ decrease in the concentration of at least 3 of the same 9 proinflammatory cytokines. Based on our prior data, we assume that no more than 10% of placebo-treated women will achieve a decrease in  $\geq 3$  of the 9 proinflammatory genital tract cytokines. Moreover, we hypothesize that at least half of the participants in the treatment arm will achieve a decrease  $\geq 1 \log_{10}$  in  $\geq 3$  of the 9 proinflammatory genital tract cytokines. With the targeted sample size of 60 randomized women (1/3 in placebo arm & 2/3 in the LACTIN-V arm; there will be more than 88% power to detect a 40% absolute difference (10% vs. 50%) in the proportion of women with decreased inflammation between the two treatment arms. This power calculation was based on simulation study using 10,000 Monte Carlo samples and two-sided Fisher's exact test with type 1 error rate of 5%.

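### Safety is a primary between-arm objective, but section 11.5 plans no estimate or interval for the excess of adverse events over placebo

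*Combined protocol and SAP*

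**What the plan says.** Section 3.3.1 lists safety and acceptability as the third primary objective. Section 3.4.1 has product-related AEs and SAEs compared by study arm, and section 4.0 makes the comparison explicit: "The study will also assess the safety of LACTIN-V by comparing the incidence of AEs between women randomized to LACTIN-V or placebo".

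Section 11.5 calls the AE and SAE analysis mainly descriptive. It plans:

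- frequencies and percentages by grade in each arm;
- intervals for rates: "Confidence intervals for AEs rates will be estimated using methods for exact binomial confidence intervals";
- a between-arm test: "Fisher's exact test will be used to compare rates of AEs between the two treatment arms";
- a logistic regression comparing the arms with adjustment for other covariates, which are not named;
- MedDRA coding of unsolicited AEs with exact 95% intervals for proportions, and a listing of SAEs.

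No significance level, sidedness, set of AEs or multiplicity rule is given for the AE test. The arm sizes in section 11.3 are "n=20 for the placebo arm A and n=40 for the LACTIN-V arm B". The only safety precision figures are in section 11.4, for all 60 women together; for example, "the probability of observing at least one incidence of AE with true rate of 5% is 0.95".

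**The concern.** A comparative safety question asks how much more often AEs occur on LACTIN-V than on placebo, and how large an excess the data leave open. Fisher's p-value answers neither part. The exact binomial intervals are for single proportions; set side by side, they do not give an interval for the difference. The logistic model could produce an odds ratio with an interval, but the plan does not commit to reporting one. The table in section 11.4 concerns the chance of seeing any event, not an excess over placebo.

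At stake is how the primary safety result can be read. In a trial this small a non-significant test is a frequent outcome even when a sizeable excess of local reactions exists. Without an interval for the difference, the report would not show how large an excess remains possible.

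**Working it through.** **Inputs.** Arm sizes are 20 and 40 (section 11.3). The two-sided 5% level is stated in section 11.3 for the cytokine endpoint only and is assumed here for AEs. The documents give no placebo AE rate for this trial. Section 2.6.1.1 gives rates from the earlier Phase 2a trial (LV-006): 46% for discharge of product, 46% for abdominal pain and 21% for dysuria. Those pool 24 women randomized 3:1 to LACTIN-V or placebo, so they are markers on a range, not placebo rates.

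**Method.** For true rates p₀ (placebo) and p₁ (LACTIN-V), power = Σₐ Σ_b Bin(a; 20, p₀) × Bin(b; 40, p₁), summed over all outcomes with two-sided Fisher p ≤ 0.05. The chance of a non-significant result is 1 − power.

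**The plan's own figures.** For 10% v 50% this gives 89.1%, in agreement with the stated power of more than 88%. For section 11.4, 1 − (1 − p)^60 gives 0.260, 0.453, 0.702 and 0.954 at true rates of 0.5%, 1%, 2% and 5%, matching the plan's 0.26, 0.45, 0.70 and 0.95. Both sets are sound, but neither concerns an AE excess between arms.

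**Chance of a non-significant test when the AE rate truly doubles (20 v 40).**

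| Placebo | LACTIN-V | Power | Non-significant |
|---|---|---|---|
| 5% | 10% | 0.018 | 98% |
| 10% | 20% | 0.115 | 88% |
| 15% | 30% | 0.192 | 81% |
| 20% | 40% | 0.285 | 71.5% |
| 21% | 42% | 0.306 | 69% |
| 25% | 50% | 0.391 | 61% |
| 30% | 60% | 0.508 | 49% |
| 35% | 70% | 0.684 | 32% |
| 40% | 80% | 0.854 | 15% |
| 46% | 92% | 0.968 | 3% |

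Sensitivity at 20% v 40%: a one-sided 5% test is non-significant 65% of the time. If only 17 and 34 women were evaluable (an assumption), the two-sided figure is 78%. For a smaller relative increase at the high rate, 46% v 69%, power is 0.357, so 64% are non-significant.

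**What an interval would show.** Newcombe's interval for d = p₁ − p₀ uses the Wilson limits (l, u) of each proportion:

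- lower = d − √[(p₁ − l₁)² + (u₀ − p₀)²]
- upper = d + √[(u₁ − p₁)² + (p₀ − l₀)²]

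*Equal observed rates, 4/20 v 8/40.* Wilson limits are 0.081 to 0.416 (placebo) and 0.105 to 0.348 (LACTIN-V), and d = 0.

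- lower = −√(0.095² + 0.216²) = −0.236
- upper = √(0.148² + 0.119²) = 0.190

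Fisher p = 1.00, yet the interval runs from −24 to +19 points. The score interval for the risk ratio is 0.37 to 2.92, so a doubling is not excluded.

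*Observed doubling, 4/20 v 16/40.* Fisher p = 0.15. The difference is +20 points (−6 to +39) and the ratio is 2.0 (0.85 to 5.3).

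**The case against.** The strongest reply is that the plan does not rest safety on a p-value. Section 11.5 describes the analysis as mainly descriptive and gives frequencies by arm, exact intervals for rates and an SAE listing. Sections 9.5 and 9.6 add halting rules and DSMB review that do not depend on significance. Low power for AE comparisons is inherent in a 60-woman Phase 2 trial sized on cytokines, and an interval adds no information to the data. Per-arm intervals also show imprecision: for 4/20 and 17/40 they are 6–44% and 27–59%.

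Much of this stands. The sample size is not the defect, and the per-arm intervals are useful. But they do not state the limits for the difference. In that same example Fisher gives p = 0.15, while the Newcombe interval for the +22.5-point difference is −3 to +42. A mainly descriptive analysis is also the setting in which an estimate with an interval is more informative than a test.

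Three stronger readings are tempting, and the documents do not support them:

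- **That the plan equates non-significance with safety.** No section says so.
- **That a doubling of a common AE is generally missed about 70% of the time.** That holds only for a placebo rate near 20%. Doubling the 46% rate in section 2.6.1.1 would be missed 3% of the time.
- **That Fisher's test is the one fully specified comparison.** Its level, sidedness and AE set are not stated, and a logistic model is planned beside it.

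**Conclusion.** The gap is real but limited: a primary, comparative safety objective has no planned estimate or interval for the between-arm difference in AE rates. The plan's stated power and detection figures are correct and are not in dispute.

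Its size depends on the unknown placebo rate. The 71.5% figure belongs to 20% v 40%, within a range of 98% to 3% for doublings from placebo rates of 5% to 46%. These figures assume a two-sided 5% Fisher test and all 60 women evaluable. The interval example needs no assumed true rate: with 4/20 and 8/40 observed, an excess of up to 19 points lies within the 95% interval while Fisher gives p = 1.00. A non-significant Fisher result therefore cannot by itself support a statement that AEs are no more frequent on LACTIN-V.

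**What to change.** In section 11.5, make the between-arm AE summary the risk difference (LACTIN-V minus placebo) with a two-sided 95% Newcombe or score interval, naming one of the two methods in advance. Report it for any AE, product-related AEs, AEs of Grade 2 or higher, AEs of Grade 3 or higher, and each solicited AE. Keep Fisher's p-value as a supplement. Add that a non-significant result is not evidence of no excess, and that the interval accompanies any statement on comparative safety.

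Do not add a rule that draws the safety conclusion from the upper limit: the plan sets no margin, so such a rule could not be applied.

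The cost is a few lines of text and one more table column, with no new data or participants. The downside is that the intervals will be wide and the safety statement more cautious.

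### For rare or near-universal AEs, the covariate-adjusted logistic regression in section 11.5 will often be inestimable with 20 v 40 women, and no sparse-data method is given

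*Combined protocol and SAP*

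**What the plan says.** The arms are small and unequal: "n=20 for the placebo arm A and n=40 for the LACTIN-V arm B" (section 11.3). Section 11.5 describes the safety analysis in these terms: "The analyses of AEs and SAEs is mainly descriptive". For rates it adds: "Confidence intervals for AEs rates will be estimated using methods for exact binomial confidence intervals". For the comparison between arms it gives two methods. The first is unadjusted: "Fisher's exact test will be used to compare rates of AEs between the two treatment arms". The second is the adjusted model: "Multivariate analyses using logistic regression models will be used to compare AEs rates between the two arms while adjusting for the effect of other covariates". The plan does not say whether that model is penalised, which covariates enter it, which AEs it covers, or what happens if it does not converge.

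On likely rates the document gives several figures. Section 11.4 tabulates the chance of seeing an event among 60 women at true rates of 0.5%, 1%, 2% and 5%, and ends: "the probability of observing at least one incidence of AE with true rate of 5% is 0.95". Section 2.6.1.1 reports the LV-006 trial at the same dose: "All enrolled women (n=24) reported at least one AE". The same section gives no Grade 3 AE or SAE in those 24 women, and rates of 46%, 46% and 21% for the commonest genitourinary AEs. Section 2.4 puts each of the main AEs of the Phase 2 capsule trial below 40%. Sections 3.4.1 and 11.2 single out Grade 3 AEs as being of particular interest.

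**The concern.** Maximum-likelihood logistic regression gives a finite arm odds ratio only if both arms contain women with the event and women without it. Each covariate adds further ways for the data to separate. When separation occurs, software may report non-convergence, or a very large coefficient with a meaningless standard error.

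Safety is one of the three primary objectives, and the AEs singled out for attention are the severe ones, which are likely to be rare. For those, the only adjusted between-arm estimate in the plan may not exist. Without a rule fixed in advance, the analyst would decide after seeing the data which AEs to model, which covariates to drop and what to do on failure. The models that happen to converge are a selected set.

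**Working it through.** **Inputs.** Arms of 20 and 40 (section 11.3). Rates of 0.5-5% (section 11.4) and of 21%, 46% and 100% (section 2.6.1.1). No dropout is assumed, because none is stated.

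**The plan's own table.** P(at least one event in 60) = 1 - (1 - p)^60. This gives 0.2597, 0.4528, 0.7024 and 0.9539 at 0.5%, 1%, 2% and 5%. The printed 0.26, 0.45, 0.70 and 0.95 all reproduce. The column label must mean one or more, since two or more would give 0.81 at 5%.

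**Unadjusted arm odds ratio.** It is infinite, zero or undefined if either arm has no events or all events. For a rare AE with rate p in both arms, the probability is 1 - [1 - (1 - p)^20] × [1 - (1 - p)^40]; the all-event terms are negligible.

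- 5%: 0.95^20 = 0.3585 and 0.95^40 = 0.1285, so 1 - 0.6415 × 0.8715 = 0.44
- 2%: 1 - 0.3324 × 0.5543 = 0.82
- 1%: 1 - 0.1821 × 0.3310 = 0.94
- 10%: 0.135
- 21%: 0.009
- 46%: about 0.000005

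The values mirror at the top end: 0.135 at 90%, 0.44 at 95%, 0.82 at 98%, and certainty at 100%. The probability exceeds one half only for rates up to about 4.4% or from about 95.6%. With unequal rates (placebo v LACTIN-V) it is 0.84 at 1% v 5%, 0.37 at 5% v 10% and 0.12 at 10% v 20%.

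**With covariates.** The plan names none, so these are assumptions: arm plus one normal and two binary covariates, all unrelated to the AE. Three sets of simulations (800 to 3,000 trials per scenario) gave the ranges below. The last column comes from the 800-trial set only.

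| Placebo v LACTIN-V | Fit fails or any separation | Arm odds ratio itself non-finite |
|---|---|---|
| 2% v 5% | 83-86% | not computed |
| 5% v 5% | 64-68% | 47% |
| 5% v 10% | 48-53% | 37% |
| 10% v 10% | 26-31% | 13% |
| 21% v 21% | 3-4% | 1% |
| 46% v 46% | 0% | 0% |
| 95% v 95% | 64-68% | not computed |

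The two result columns differ because a covariate can separate the data while the arm odds ratio stays finite. A further 600-trial run gave any separation in 61% of trials at 5% with two covariates and 74% with four.

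**Fits that converge.** At 5% v 10% the true log odds ratio is ln[(0.10/0.90)/(0.05/0.95)] = 0.75. Converged fits averaged 0.30 to 0.33. At 5% v 5%, where the truth is 0, they averaged -0.29. The cause can be seen by hand. The smaller placebo arm is the more likely to have no events, and those trials drop out. Given at least one event, the mean placebo rate at a true 5% is (1/0.6415)/20 = 7.8%, and the mean LACTIN-V rate is (2/0.8715)/40 = 5.7%. The selection therefore makes LACTIN-V look safer than it is.

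**Firth's penalised likelihood.** It converged in at least 99.9% of runs. It averaged 0.52 to 0.61 at 5% v 10% (truth 0.75) and -0.05 at 5% v 5% (truth 0).

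**The case against.** A reader who sets the 0.5-5% table beside LV-006's 24 of 24 might infer that AE outcomes lie at the extremes, so that the odds ratio is infinite or undefined in most plausible cases. The documents do not support that. The same LV-006 paragraph gives AEs at 46%, 46% and 21%, and the capsule trial's main AEs were each below 40%. Such AEs are natural candidates for a regression, and the model fits there. The section 11.4 table concerns the chance of detecting an event; it does not forecast the rates of the outcomes to be modelled. Even at 5% the unadjusted odds ratio is finite in 56% of trials.

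A reader might also infer that the safety comparison collapses. It does not. Fisher's test and the exact binomial intervals work with zero cells. The analysis is declared mainly descriptive, and in a randomised trial the unadjusted comparison is valid. Decisions to halt rest on event counts and DSMB review (sections 9.5 and 9.6), not on this model.

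Three smaller points are fair. The plan does not say unpenalised maximum likelihood, so a Firth fit is compatible with its text. Firth estimates are themselves shrunk, and the maximum-likelihood averages above cover converged fits only. A risk difference with an interval is a reporting request as much as a remedy for separation.

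What remains is narrower. The commitment to logistic regression is unconditional, it gives no fallback for the AEs where the usual fit often fails, and the intervals it specifies are for AE rates, with none stated for the difference between arms.

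**Conclusion.** The concern holds for AEs with a true rate of about 5% or less or about 95% or more, if the model is fitted by ordinary maximum likelihood. There the unadjusted arm odds ratio fails to exist with probability 0.44 at 5%, rising to 0.82 at 2% and 0.94 at 1%. With three covariates, some separation occurs in roughly 60-70% of trials at 5% v 5%. Estimates from the fits that do converge are biased in LACTIN-V's favour in the two scenarios examined. It is not a concern at 21-46%, and it leaves the main unadjusted comparison intact. This makes it a worthwhile, inexpensive correction to a supporting analysis.

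The result rests on equal true rates unless stated, full follow-up, and covariates whose number and type are assumed. Two points about rates are uncertain. LV-006's 0 of 24 for Grade 3 suggests a low rate without proving one below 5%: at a true 10%, 0 of 24 would still occur with probability 0.9^24 = 0.08. And the 21% and 46% figures are not stated to be product-related; product-related rates could be lower, which would move some AEs towards the sparse range.

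**What to change.** In section 11.5:

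1. State that Fisher's exact test is the main between-arm AE comparison.
2. Beside each Fisher p-value, report the unadjusted risk difference with an exact unconditional or Miettinen-Nurminen 95% confidence interval. It exists when an arm has no events, which the odds ratio does not.
3. Fit the adjusted AE models by Firth penalised logistic regression with profile-likelihood confidence intervals.
4. Name the covariates and the AE outcomes to be modelled before unblinding, and keep the covariates few. Expected events are 60 × 0.21 = 12.6 at a 21% rate and 60 × 0.46 = 27.6 at 46%. A rule of thumb of ten events per parameter (an assumption, not in the documents) then allows about one to three parameters including arm.
5. Where no woman or every woman has the AE, report counts only. With no events at all, an unadjusted Firth fit amounts to adding 0.5 to each cell and returns an odds ratio of (0.5/40.5)/(0.5/20.5) = 0.51, which reflects only the arm sizes.

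The cost is SAP wording and a little more analysis work, using methods available in standard software. The statistical price is slight shrinkage of the adjusted odds ratio towards 1. Sample size, data collection and clinical procedures do not change.
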